# C. Study Design and Research Methods

## Study Design:

This study will be a prospective non-randomized cohort study with patients presenting to Children's Hospital Colorado for resection of a central nervous system tumor. Due to heterogeneity of the pediatric central nervous system tumors and the evidence available, we will have a planned initial cohort (first phase) that will include tumor pathology that will allow us to test the feasibility of the study and the preliminary activity of fluorescein in the pediatric population. After completion of this initial cohort, we will expand our study to include tumors that are more specific to the pediatric population.

Currently, there exist many tumor types where there is robust literature on the use of fluorescein [3,4,6-15,21-26,27-29]. We plan to enroll patients based on a phased system and after completion of the first phase, we will perform a safety analysis as outlined below.

[name]: 18-0242 Page 3 Version: 07/03/2019

After safety analysis is completed, we will either proceed to the next phase, or in the event there is a safety concern, the DSMC will terminate our study. Terms for termination are detailed below.

Enrollment of ten patients is planned for each tumor type in each of the phases. The phases are designed to assess patients where evidence is available and proceed to tumor types where pediatric evidence is limited and the tumors are more unique to the pediatric population. This will allow us to safely assess patients and allow us to expand our trial in a controlled fashion. After completion of each phase of enrollment, we will continue enrolling the prior phase patients for a maximal total of 10 patients per each pathology group. Thus, maximal enrollment will be 20 patients for the first phase pathologies and 30 patients for the second phase pathologies, for a total enrollment of 50 treated patients and 150 historical controls

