[name]: 18-0242 Page 6 Version: 07/03/2019

physical, neurologic exam data, and may also include laboratory findings and post-operative imaging studies. These will all be documented clinically and recorded via chart review for the study. Patients will be followed for the study through Month 2 (or 8 weeks) post-surgery.

Furthermore, any adverse events occurring after surgery will be collected until 7 (for non-serious AEs) or 30 days (for SAEs) after the last day of study intervention (administration of fluorescein). All adverse events will be followed for outcome information until resolution or through Month 6 post-surgery.

For example, if a patient has no adverse events following surgery, they will only be followed through end of study period which is 2 months post-surgery. If the patient had adverse events within the first 30 days, those adverse events will be followed through resolution or 6 months post procedure, whichever comes first.

Re-Enrollment: Patients who have previously been enrolled in this study and received prior administration of fluorescein sodium as a part of this study for guided tumor resection are eligible for re-enrollment into the study, should further surgical resection be clinically indicated. Patients will receive the same dosage as outlined in the protocol of 3mg/kg. Clearance of 500mg of fluorescein sodium is 24-72 hours after administration of a single dose [16]. Patients re-enrolled into the study will be eligible after 3 days given the clearance time necessary for fluorescein sodium. Patients will be enrolled with the same study number. Patients will be reconsented at time of re-enrollment.

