Given this, we propose a 3:1 ratio of historical controls to fluorescein treated patients to match tumor location and histology. 150 historical controls will be pulled from the last ten years of Children's Hospital patients and matched to the 50 fluorescein treated cases on lesion location and pathology. This 3:1 ratio will strengthen our ability to objectively assess for adverse events related to sodium fluorescein as well as our extent of tumor resection analysis. Importantly, historical controls undergo stereotactic-guided tumor resection in a similar fashion to patients undergoing fluorescein administrations as outlined in our protocol.

All patients who undergo sodium fluorescein-aided resection will also have neuropathological analysis. We will analyze correlation of fluorescein staining to histopathology. Tissue obtained during the time of surgery will be used to correlate fluorescein staining to histopathological diagnosis. This data will be used to calculate sensitivity and specificity of fluorescein staining for tumors. Pre- and post-operative imaging will be used to assess the degree of the extent of resection in intraparenchymal tumors. Data collected from post-operative follow-up will be used to assess for potential complications/adverse reactions associated with sodium fluorescein administration.

For data analysis, extent of tumor resection will be compared as a continuous value across groups using a parametric ANOVA. Further calculations, such as sensitivity, specificity and positive predictive value will be calculated by contingency tables. Additionally, since group membership is not random we will run an adjusted analysis predicting the likelihood of tumor resection as a continuous outcome adjusting for demographic and co-morbidity factors. Significance will be assigned at p < 0.05.

Furthermore, adverse reactions and population/demographic data will be characterized using relative risk and odds ratios. Overall survival and progression free survival analysis will be characterized using Kaplan-Meier curves and compared across groups using a log rank test.

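### The log-rank test for overall and progression-free survival names no strata although controls are matched on pathology; if survival is followed beyond Month 2, stratify by tumour group

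*Combined protocol and SAP*

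**What the plan says.** The survival analysis is one sentence in section F: "Overall survival and progression free survival analysis will be characterized using Kaplan-Meier curves and compared across groups using a log rank test". The same section sets the criterion: "Significance will be assigned at p < 0.05". It names no strata, matched-set method or Cox model for survival. The only adjusted analysis in section F is for extent of resection, and its covariates are demographic and co-morbidity factors.

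The design is built around tumour type. Under Study Design, "Enrollment of ten patients is planned for each tumor type in each of the phases", and "maximal enrollment will be 20 patients for the first phase pathologies and 30 patients for the second phase pathologies". Section F draws 150 controls from the last ten years, "matched to the 50 fluorescein treated cases on lesion location and pathology".

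On follow-up, the Follow-Up paragraph of section IV.C says "Patients will be followed for the study through Month 2 (or 8 weeks) post-surgery". Anything longer is for unresolved adverse events only: "those adverse events will be followed through resolution or 6 months post procedure, whichever comes first".

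Section IV.A (Outcome Measures) does not list overall or progression-free survival as a primary or secondary outcome. No event target, hazard ratio or power is given for either.

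**The concern.** Matching fixes the treated-to-control ratio within each pathology. The survival test as written then takes no account of pathology. The groups run from high grade glioma to pilocytic astrocytoma, so large differences in event rates are likely.

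The plain log-rank variance treats everyone at risk as exchangeable. When the cohorts are balanced on a strong prognostic factor, that variance is too large for the numerator, so the p-value tends to be too large. High-risk patients also leave the risk set early, which pulls the pooled effect towards no difference.

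If follow-up is not similar across types and cohorts, the balance is lost over time and the pooled test can be shifted in either direction. Pooled Kaplan-Meier curves would also describe a mixture of tumours that represents no single group.

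**Working it through.** **The plan's own figure.** The only sample-size result is Table 3, for extent of resection. With a difference of 16, SD 25, f = 16/(2 × 25) = 0.32, equal groups and a noncentral F, the totals are 64, 80 and 106 for 70%, 80% and 90% power. These match Table 3 exactly, but say nothing about survival.

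**Design inputs.** Five tumour groups, each with 10 treated and, at 3:1, 30 controls: 5 × 40 = 200 patients, 25% treated. Alpha is 0.05, taken as two-sided because the plan does not say.

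**Events needed.** The Schoenfeld formula is events = (1.960 + 0.842)² / [0.25 × 0.75 × (ln HR)²] for 80% power.
- HR 0.5: 7.85 / (0.1875 × 0.4805) = 87.1, so 88 events.
- HR 0.7: 7.85 / (0.1875 × 0.1272) = 329.0, so 330 events.

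**The two tests.** Unstratified: Z = Σ(g − p) / √Σp(1 − p), summed over events. Here g marks a treated patient and p is the treated share of everyone at risk. Stratified: the same sums, with p taken within tumour group, then added over the five groups.

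**Assumed rates.** The documents give no survival rates, so three sets of 2-year event-free rates were assumed, in the order high grade glioma / pilocytic astrocytoma / medulloblastoma / ependymoma / spinal. Survival was exponential with equal administrative follow-up, 5,000 runs per setting (Monte Carlo error at most about 0.7 points). Power is unstratified vs stratified.

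| Spread (2-year rates, %) | HR 0.5, 24 months | HR 0.5, 60 months | Unstratified null rejection, 24 / 60 months |
|---|---|---|---|
| Strong (20/90/70/70/80) | 39% vs 54% | 59% vs 80% | 2.1% / 2.1% |
| Moderate (35/95/75/75/85) | 34% vs 43% | 53% vs 72% | 2.7% / 2.0% |
| Mild (50/90/75/75/80) | 38% vs 42% | 67% vs 74% | 4.1% / 3.3% |

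Stratified null rejection was 4.7-5.3%. The gains are 15, 9 and 4 points at 24 months and 21, 19 and 7 at 60 months. A repeat run of the strong case at 60 months gave 59% vs 81%, hence 4-22 overall.

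**Smaller effect.** At HR 0.7 and 24 months: 10.7% vs 19.0%, 9.5% vs 14.0% and 14.2% vs 16.3%. At 60 months the gain reaches about 16 points, but stratified power is still only 26-31%.

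**Other assumed rates.** A second, independent set used 1-year rates with ranges 60-95%, 35-99% and 20-99.5%. At 5 years and HR 0.5, power was 64% vs 77%, 42% vs 78% and 27% vs 79%, with unstratified null rejection of 2.9%, 1.0% and 0.2%. With equal prognosis (80% in every group) it was 87% vs 87%, so stratifying cost nothing.

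**On the written schedule.** A 2-year rate S gives a 2-month event probability of 1 − S^(1/12). For the strong spread with no effect, expected events are 40 × (0.1255 + 0.0087 + 0.0293 + 0.0293 + 0.0184) = 8.4 in 200 patients, about a quarter of them treated. Power at HR 0.5 is 1.1% vs 1.6%, 0.5% vs 0.6% and 0.4% vs 0.4% (strong, moderate, mild). Even the widest alternative spread gives only 4.4% vs 6.8%.

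**Unequal follow-up.** Assume treated follow-up of 3-5 years in phase 1 and 0.2-2 years in phase 2, with 1-10 years for controls.
- If the phase 1 types have the better prognosis (1-year rates 90/95/35/60/80), unstratified null rejection is 13.0%, with mean Z −1.07 in favour of fluorescein. Stratified it is 5.2%.
- If high grade glioma is the worst group, as in the second set of rates, unstratified rejection is 0.2-2.4% with mean Z between −0.33 and 0.19. Stratified it is 5.0-5.2%.

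The first case shows what can happen and is not a forecast, since phase 1 includes high grade glioma.

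**The case against.** The strongest objection is that the protocol's own follow-up ends at Month 2, where neither test has usable power. A reader might infer that the plan as written gives away a large amount of power. The documents do not support that: the gains arise only with longer follow-up, which the protocol does not provide. This objection stands, and the point is conditional on it.

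A reader might also infer that the test is simply conservative. That needs similar follow-up across cohorts and types, which phased enrolment and ten years of historical controls do not assure. At Month 2 most of the shortfall below 5% comes from sparse events, not from pooling.

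The plan does not say that types are pooled. That is the natural reading of a log-rank test named without strata, but the comparison groups are not defined and section IV.A lets additional outcomes vary by tumour. A separate analysis by type is not ruled out; if one is intended, the sentence should say so.

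The hazard ratio and survival rates are assumed. Section II cites a glioma study with gross total resection of 83% vs 55% but no significant survival difference, so HR 0.5 is optimistic. At HR 0.7 the comparison stays weak with either test.

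Finally, strata of exactly 10 and 30 are idealised. Ten is a maximum per group, and section F expects about one tenth of patients to have spinal tumours. The spinal group is a location rather than a pathology, so a spinal ependymoma could fit two groups. These points affect how strata are defined, not whether to stratify.

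**Conclusion.** The point holds conditionally and is minor. The survival test carries no strata although the controls are matched on location and pathology. If survival is followed beyond Month 2, the unstratified test does not hold its 5% level.

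- **Similar follow-up in both cohorts:** true level about 2-4% under the main assumed rates, lower with wider spreads. Power lost is about 4-22 points at HR 0.5, about 2-16 points at HR 0.7, and none if prognosis is equal across groups.
- **Follow-up differing by type and cohort:** it can be biased or anti-conservative.
- **Month 2 schedule:** almost no difference, because events are too few for either test.

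The sizes rest on assumed survival rates and hazard ratios, exponential survival and full 10:30 groups. A reader might take this as a threat to the trial's main result. It is not: the primary outcome is extent of resection, and survival is an unlisted outcome. Stratifying also leaves era and selection differences between historical and treated patients untouched.

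**What to change.** In section F, replace the plain log-rank test with one stratified by tumour group, and report the hazard ratio from a Cox model stratified in the same way. Show Kaplan-Meier curves by group as well as pooled.

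Define the strata in the same sentence. Each treated patient and control belongs to exactly one group, assigned by the same rule in both cohorts and consistent with the matching on location and pathology, with spinal tumours as their own group. State whether the enrolment diagnosis or the final pathology governs if they differ.

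The change is useful only if survival follow-up beyond Month 2 is defined for both cohorts. If it is not, the plan should say that the survival comparison is descriptive.

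The cost is a sentence or two. Stratifying needs no new data, because pathology and location are already the matching variables, and with five strata of about 40 patients the loss from stratifying is negligible. Naming the strata in advance also removes a choice that could otherwise be made after seeing the data.

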# G. Adverse Events and Unanticipated Problems:

#### 1. Adverse Events and Serious Adverse Events

#### a. Definition of Roles:

- Sponsor: person listed in field 1 of form FDA 1571
- Site Principal Investigator: person listed in field 1 on form FDA 1572
- Licensed Independent Practitioner (LIP): MD with current Colorado Medical License

## b. Definition of Adverse Events (AE)

Adverse event means any untoward medical occurrence associated with the use of a drug in humans, whether or not considered drug related (21 CFR 312.32 (a))

## c. Definition of Serious Adverse Events (SAE)

An adverse event (AE) or suspected adverse reaction is considered "serious" if, in the view of either the Site Principal Investigator or Sponsor, it results in any of the following outcomes:

- death,
- a life-threatening adverse event,

[name]: 18-0242 Page 9 Version: 07/03/2019

- inpatient hospitalization or prolongation of existing hospitalization,
- a persistent or significant incapacity or substantial disruption of the ability to conduct normal life functions, or
- a congenital anomaly/birth defect.
- Important medical events that may not result in death, be life-threatening, or require
  hospitalization may be considered serious when, based upon appropriate medical
  judgment, they may jeopardize the participant and may require medical or surgical
  intervention to prevent one of the outcomes listed in this definition.

## d. Classification of an Adverse Event

# i. Severity of Event:

A study team member, who is a Licensed Independent Provider (LIP) will be responsible for determining the severity of each AE.

For adverse events (AEs), the following guidelines will be used to describe severity:

- Mild Events require minimal or no treatment and do not interfere with the participant's daily activities.
- **Moderate** Events result in a low level of inconvenience or concern with the therapeutic measures. Moderate events may cause some interference with functioning.
- **Severe** Events interrupt a participant's usual daily activity and may require systemic drug therapy or other treatment. Severe events are usually potentially life-threatening or incapacitating. Of note, the term "severe" does not necessarily equate to "serious".]

# ii. Relationship to Study Intervention:

A study team member, who is a Licensed Independent Provider (LIP) will be responsible for determining the relationship of each AE to the study intervention.

- Definitely Related There is clear evidence to suggest a causal relationship, and other
  possible contributing factors can be ruled out. The clinical event, including an abnormal
  laboratory test result, occurs in a plausible time relationship to study intervention
  administration and cannot be explained by concurrent disease or other drugs or chemicals.
  The response to withdrawal of the study intervention (dechallenge) should be clinically
  plausible. The event must be pharmacologically or phenomenologically definitive, with use
  of a satisfactory rechallenge procedure if necessary.
- **Probably Related** There is evidence to suggest a causal relationship, and the influence of other factors is unlikely. The clinical event, including an abnormal laboratory test result, occurs within a reasonable time after administration of the study intervention, is unlikely to be attributed to concurrent disease or other drugs or chemicals, and follows a clinically reasonable response on withdrawal (dechallenge). Rechallenge information is not required to fulfill this definition.
- Potentially Related There is some evidence to suggest a causal relationship (e.g., the event occurred within a reasonable time after administration of the trial medication). However, other factors may have contributed to the event (e.g., the participant's clinical condition, other concomitant events). Although an AE may rate only as "possibly related" soon after discovery, it can be flagged as requiring more information and later be upgraded to "probably related" or "definitely related", or downgraded to ..., as appropriate.
- Unlikely to be related A clinical event, including an abnormal laboratory test result, whose temporal relationship to study intervention administration makes a causal relationship improbable (e.g., the event did not occur within a reasonable time after administration of the study intervention) and in which other drugs or chemicals or underlying disease provides plausible explanations (e.g., the participant's clinical condition, other concomitant treatments).
- **Not Related** The AE is completely independent of study intervention administration, and/or evidence exists that the event is definitely related to another etiology. There must be an alternative, definitive etiology documented by the

[name]: 18-0242 Page 10 Version: 07/03/2019

#### iii. Expectedness:

A study team member, who is a Licensed Independent Provider (LIP) will be responsible for determining whether an AE is expected or unexpected.

An AE will be considered unexpected if the nature, severity, or frequency of the event is not consistent with the risk information previously described for the study intervention.

## e. Time Period and Frequency for Event Assessment and Follow Up

21 CFR 312.64(b) requires that the Site Principal Investigator records non-serious adverse events and reports them to the Sponsor according to the timetable for reporting specified in the protocol.

A properly delegated study team member will record all adverse events with start dates occurring any time after administration of fluorescein until 7 (for non-serious AEs) or 30 days (for SAEs) after the last day of study intervention. All events will be followed for outcome information until resolution or stabilization or through Month 6 post-surgery.

All AEs occurring while on study will be documented regardless of their relationship to the study intervention, and whether or not they meet the definition of an SAE. AEs will be captured, reviewed and assessed by an LIP member of the study team. The outcome of this review and assessment will be documented by a properly delegated study team member on an Adverse Event Log. Information to be collected includes event description, time of onset (start date) and time of resolution/stabilization of the event (end date), and the LIP's assessment of expectedness, severity and relationship to study intervention.

Any medical condition that is present at the time the participant is screened will be considered as baseline medical history, and will not be recorded as an AE. However, if the study participant's condition deteriorates at any time during the study, the event will be recorded as an AE.

Changes in the severity or frequency of an AE will be documented as separate events to allow an assessment of the duration of the event at each level of severity or frequency.

AEs characterized as intermittent will be documented with onset and duration of each episode.

At each study visit, a properly delegated study team member will document all occurrences of AEs and SAEs since the last visit. This information will be gathered through direct observation (e.g. rash), elicited from or spontaneously volunteered by the participant, documentation in Medical Records, laboratory or other clinical reports or notes, or identified in patient-reported outcome tools (e.g. diaries, surveys, questionnaires), or any other means.

## f. Adverse Event Reporting

Adverse Event Reporting will be performed in accordance with the study protocol, any contractual agreement, and all IRB requirements.

21 CFR 312.64(b) requires that the Site Principal Investigator records non-serious adverse events and reports them to the Sponsor according to the timetable for reporting specified below.

**Disease-Related Events (DREs):** The following disease-related events (DREs) are expected and common with brain tumor surgery, and will not be reported per the standard process for adverse event reporting: bleeding in the brain, injury or swelling to the brain, infection in the brain or at wound site, meningitis, seizures, hydrocephalus, cerebral spinal fluid leakage, the need for

[name]: 18-0242 Page 11 Version: 07/03/2019

additional surgery, tearing of the eyes, damage to the eye, blood clots, stroke, dizzy spells, recurrence or tumor growth, postoperative pain and allergic reactions to anesthesia.

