#### Calculation for GFR

$$\mathit{GFR} = \frac{0.41*\mathit{Height\ in\ cm}}{\mathit{Serum\ Creatinine\ in\ mg/dL}}$$

The exclusion criteria "pregnant or nursing mother" will be evaluated for females of childbearing potential. We will utilize Children's Hospital Colorado's perioperative definition of childbearing potential as females who have reached menarche or are 12 years of age or older. Pregnancy testing is standard of care for these patients and pregnancy test results will be evaluated through chart review.

[name]: 18-0242 Page 5 Version: 07/03/2019

<sup>1See Follow Up section below for more detail

Pre-operative Evaluation: A standard of care neurosurgical assessment will occur at admission: standard clinical evaluation for tumor including pertinent history, physical and neurologic exam data, laboratory findings, and initial imaging studies will all be documented clinically and recorded via chart review for the study.

Imaging: Patients will have pre- and post-operative imaging in accordance with the standard clinical procedures at Children's Hospital Colorado. Patients in this study will not require any study-specific imaging outside the standard of care. All post-operative images are reviewed by fellowship trained pediatric specific neuroradiologists. Neuroradiologists are not informed on the administration of sodium fluorescein and will conduct review of the post-operative imaging per standard protocol. No imaging evidence of sodium fluorescein is visible on post-operative MR or CT imaging and the independent neuroradiologist is blinded to the operative course of the patient.

Sodium Fluorescein Administration: Patients enrolled in this study will receive 3 mg/kg sodium fluorescein following induction of anesthesia by administration into a peripheral venous line over 10 seconds. This dose has been previously reported for use in a pediatric population and has been studied in adult tumor population [15]. Previous studies have used doses ranging from 500mg standing to 20mg/kg with minimal side effects [7]. The FDA-approved dosage for children is 7.7 mg/kg intravenously. A lower dose and earlier administration reduces the incidence of fluorescent contamination of normal brain. Furthermore, the advent of new neurosurgical microscopes with fluorescein filters decreases the dosage required to observe fluorescence.

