# D. Description, Risks and Justification of Procedures and Data Collection Tools:

Potential Risks: Studies have examined the risk of using fluorescein for multiple purposes with no serious side effects [21]. The FDA has already approved the use of sodium fluorescein in adults and children for diagnostic angiography of the retina and it is also widely used as a contrast agent. The dose and route of administration being used in this study are consistent with the FDA approval for use of this drug in children.

The use of intravenous sodium fluorescein in gastrointestinal procedures has been reported to be extremely safe. Side effects from these studies include nausea/vomiting, injection site erythema, rash, and epigastric pain. Other investigators have examined the safety profile of intravenous fluorescein use in angiography. In these studies, reported potential side effects of sodium fluorescein administration include, urticaria, syncope, respiratory reactions, cardiac reactions, and hypersensitivity reactions. Multiple mechanisms have been suggested such as vasovagal phenomenon, histamine release via a nonallergic pathway, and sympathetic discharge related to anxiety as the pathogenetic basis of these side effects. The most common symptoms (>20%) reported in these studies include malaise, headache, dizziness, and nausea/vomiting [22-24].

A reported side effect of Fluorescein is yellowish skin for 6-12 hours after administration and yellow urine for 24-36 hours after administration. Fluorescein is systemically cleared by 48 to 72 hours after administration.

The package insert for Fluorescein describes "care must be taken to avoid extravasation during injection as the high pH of fluorescein solution can result in severe local tissue damage." To alleviate this risk, the medication will be given IV push over 10 seconds.

Confidentiality of Study Data: Data including enrollment, study drug orders, pre-operative and postoperative exams and adverse event reporting will remain identifiable. De- identification of this information is not possible as patient identifying information is necessary for continued

[name]: 18-0242 Page 7 Version: 07/03/2019

patient safety monitoring and follow-up while in the trial.

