# g. Serious Adverse Event Reporting

The Site Principal Investigator will immediately report to the Sponsor any serious adverse event, whether or not considered study intervention related, including those listed in the protocol or investigator brochure, and will include the study team LIP's assessment of whether there is a reasonable possibility that the study intervention caused the event.

Study endpoints that are serious adverse events (e.g. all-cause mortality) will be reported in accordance with the protocol unless there is evidence suggesting a causal relationship between

[name]: 18-0242 Page 12 Version: 07/03/2019

the study intervention and the event (e.g., death from anaphylaxis). In that case, the Site Principal Investigator must immediately report the event to the Sponsor.

All SAEs will be followed until satisfactory resolution or until the study team's LIP deems the event to be chronic or the participant is stable.

Serious adverse events that are considered related (i.e., determined to be possibly, probably, or definitely related) to the investigational product by the Sponsor will be followed until the event resolves or stabilizes. Any SAE that occurs after treatment completion, and is considered by the Sponsor to be related to the investigational product, will be documented and reported as appropriate.

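### The exemption of listed surgical events from AE reporting has no exception for non-serious events suspected to be due to fluorescein

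*Combined protocol and SAP*

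**What the plan says.** Section IV.G.1.f (Adverse Event Reporting) gives a list of disease-related events that are "expected and common with brain tumor surgery, and will not be reported per the standard process for adverse event reporting". The list ends with "dizzy spells, recurrence or tumor growth, postoperative pain and allergic reactions to anesthesia". The section names no other process for these events and has no clause that returns an event to standard reporting when the dye is suspected.

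Section IV.D (Potential Risks) describes the dye's own effects. Its potential side effects include "urticaria, syncope, respiratory reactions, cardiac reactions, and hypersensitivity reactions". The most common symptoms, put at more than 20%, "reported in these studies include malaise, headache, dizziness, and nausea/vomiting". On timing, Section IV.C (Sodium Fluorescein Administration) says that patients "will receive 3 mg/kg sodium fluorescein following induction of anesthesia".

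Two provisions limit the exemption. Section IV.G.1.e states: "All AEs occurring while on study will be documented regardless of their relationship to the study intervention". Each logged AE also receives a physician's assessment of severity, expectedness and relatedness. Section IV.G.1.g requires immediate reporting to the Sponsor of "any serious adverse event, whether or not considered study intervention related, including those listed in the protocol or investigator brochure".

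Section IV.H sends SAEs, unanticipated problems (UAPs) and reportable AEs to the DSMC within 5 business days, asks for a DSM report every 6 months, and requires DSMC approval before the second phase.

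**The concern.** An exemption for the ordinary complications of brain tumour surgery is reasonable, since it keeps background events from swamping the safety reports. It works less well when a listed event is also a known effect of the study drug, because the list goes by type of event and not by cause. If a physician grades a non-serious dizzy spell as probably due to fluorescein, the text still says that it is not reported in the standard way.

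What is at stake is the information available at one decision. Phase 1 plans 10 patients in each of two tumour types, 2 × 10 = 20 in all, and the DSMC then reviews safety before tumour types with less paediatric evidence are opened. The risk criterion under Study Stopping Criteria is expressed through reported AEs, SAEs and UAPs. An event that is logged but not reported may not enter that judgement.

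**Working it through.** No arithmetic applies. The check is to follow the two listed events that overlap the dye's stated effects through each route in the plan.

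**Overlap of the list with the dye's effects**

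- *Dizziness.* Dizzy spells are on the exempt list without qualification, and Section IV.D names dizziness as a common effect of the dye. The overlap is direct.
- *Allergy.* The exempt item covers allergic reactions to the anaesthetic only. A reaction attributed to fluorescein is outside it and stays in standard reporting. The overlap arises only by misattribution, which is possible because the dye is given after induction and both agents are then on board.

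**Routes by which a non-serious listed event could reach the DSMC or another body**

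| Route | What it takes | Does it catch the event? |
|---|---|---|
| AE log (IV.G.1.e) | All AEs, with relatedness; non-serious ones up to 7 days after dosing | Recorded, but the log is not itself a report |
| SAE reporting (IV.G.1.g, IV.H) | Any serious event, listed or not | No, because the event is not serious |
| UAP reporting (IV.G.1.f.ii, IV.G.2) | Events that are unexpected, related, and harmful or a risk | Normally no (see below) |
| Reportable AEs to the DSMC (IV.H) | Not defined in the documents | Unclear; read with the exemption, probably not |
| 6-month DSM report (IV.H) | A toxicity summary with specific AEs | Does not say whether listed events are included |
| DSMC audit (IV.H) | Source data verification | Could find the log entry; no timing is given relative to the phase 2 decision |
| Annual FDA summary (IV.G.1.f.iii) | Most frequent and most serious AEs | Does not say whether listed events are included; goes to the FDA |
| Final analysis (IV.F) | Adverse reactions, compared with historical controls | May include it, but too late for the phase 1 decision |

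On the UAP route, Section IV.G.1.d.iii states: "An AE will be considered unexpected if the nature, severity, or frequency of the event is not consistent with the risk information previously described". Dizziness and hypersensitivity are already described as dye risks, and the exempt list itself calls its events expected. An excess in severity or frequency could still make such an event unexpected, but to see an excess in frequency someone has to count the events.

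**Comparison within the plan.** Section IV.G.1.g has a causal exception for study endpoints that are SAEs: special handling stops when evidence points to the intervention, with fatal anaphylaxis as the example. Section IV.G.1.f has no counterpart for non-serious listed events.

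**Result.** A non-serious dizzy spell graded related to fluorescein has no stated route to the DSMC before the phase 1 decision. The same holds for a mild allergic reaction once it has been filed as anaesthetic.

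**The case against.** The strongest reply is that the exemption limits itself. It covers disease-related events, and an event that a physician grades definitely or probably related to fluorescein is hard to call disease-related. On that reading only an explicit sentence is missing. This has force, but the list works by naming events, and the plan spells out a causal exception elsewhere when it wants one.

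A second reply is that little is left. The SAE definition includes important medical events that may need intervention, so a clinically important allergic reaction under anaesthesia would plausibly count as serious and be reported. This stands. The remainder is non-serious dizziness and mild reactions such as urticaria.

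A third is that the plan defers to IRB requirements, a DSMB charter and a monitoring plan. These are not in the documents and may define what is reportable. This also stands, and it limits how firm the conclusion can be.

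A reader might infer more than the text supports:

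- *That serious dye reactions could be kept from the DSMC.* The SAE rules and Section IV.H rule this out.
- *That allergic reactions in general are exempt.* Only those to the anaesthetic are.
- *That data would be lost.* Every AE is logged and graded.
- *That a child with a dye reaction could be re-dosed after 3 days.* A known fluorescein allergy is an exclusion criterion, so this would need a reaction that was not recognised as due to the dye.
- *That the gap can be sized from binomial limits on 20 or 50 patients, or from the figure of more than 20%.* The limits say nothing about how often events would be withheld. The percentage comes from angiography studies and need not carry over to 3 mg/kg given under anaesthesia.

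**Conclusion.** The concern holds in a narrow form. The exemption has no exception for non-serious listed events suspected to be due to fluorescein. It affects dizziness directly and mild allergic reactions only by misattribution. Such events could be in the AE log but absent from the reports the DSMC uses at the phase 1 decision.

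The size cannot be given as a number: the documents contain no rate for hypersensitivity and nothing on how often an event would be misfiled or left out. The conclusion assumes that the exemption is applied as written and that no charter or monitoring plan outside the documents closes the gap. It is a drafting improvement worth making because it is cheap. It is not evidence that the trial is unsafe.

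**What to change.** Add to the disease-related events paragraph in Section IV.G.1.f:

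*This exemption does not apply to any listed event graded probably or definitely related to fluorescein, nor to any allergic or hypersensitivity reaction after fluorescein injection, whatever its suspected cause. These are reported to the DSMC as reportable AEs.*

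In Section IV.H, state that the 6-month DSM report and the phase 1 safety report tabulate the remaining listed events from the AE log, including those graded potentially related. Tabulation is enough for that grade: it can rest on plausible timing alone, and individual reporting of all such events could largely undo the exemption. No clause for serious events is needed, because they are already covered.

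The change uses the existing log, relatedness grades and DSMC reports, and collects no new data. Its cost is a short amendment and a few extra reports, some of which will prove to be true anaesthetic reactions. If a charter or monitoring plan already contains these rules, a cross-reference to it is enough.
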